Study design	
This will be a confirmatory, prospective, randomised, controlled, parallel group, open-label, multi-centre phase III study to evaluate

	
the efficacy and safety of <math>^{177}\text{Lu}</math>-edotreotide in comparison to molecular targeted therapy with everolimus in patients with inoperable, progressive, somatostatin receptor-positive (SSTR+), neuroendocrine tumours of gastroenteric or pancreatic origin (GEP-NET).
 
In total, 300 GEP-NET patients will be randomised in 2:1 fashion to receive either
 
 
• PRRT with <math>^{177}\text{Lu}</math>-edotreotide consisting of a maximum of four cycles (<math>7.5 \pm 0.7</math> GBq <math>^{177}\text{Lu}</math>-edotreotide, each), administered as IV infusion at 3-monthly intervals for 9 months, or until diagnosis of progression (200 patients), or
 
• 10 mg everolimus (Afinitor®) daily, administered orally as a tablet until diagnosis of progression (100 patients)
 
 
Study duration per patient will be 30 months. Collection of survival data and information on further antineoplastic treatments as well as the development of secondary malignancies will be continued for 5 years (60 months) after EOS.
 
The primary endpoint is progression-free survival (PFS). Diagnosis of progression and liver tumour burden will be established based on radiological information from morphological imaging (MRI and/or CT) according to RECIST 1.1. Stratification will be made for primary tumour origin (GE-NET vs. P-NET) and prior medical therapy (1st line vs. 2nd line). Tumour grade (G1, G2), and baseline Karnofsky score will be used for further statistical subgroup analyses.
 
Secondary endpoints include parameters of morphological and biomarker tumour response such as objective response rate (ORR), overall survival (OS), disease control rates (DCR), as well as duration of disease control (DDC), safety, health-related quality of life (HRQL). Furthermore, exploratory analyses will be performed on patient and tumour characteristics, as well as the degree of <math>^{177}\text{Lu}</math>-edotreotide uptake for traits predicting PRRT efficacy.
 
The study is designed to confirm the trial hypothesis of a progression-free survival benefit, relative to comparator with a power of at least 0.8 and significance level (p) of <0.05 (two-sided). The sample size will also be sufficient, to confirm a progression-free survival benefit with a power (P) of 0.90 and significance level (p) of <0.01 (two-sided), if the difference in mPFS is more than 11 months.
 
Patients with histologically confirmed diagnosis of GEP-NET will be recruited globally by approximately 60 oncological centres specialised in endocrinology or gastroenterology, and with local access to or own experience in PRRT. Confirmatory histology from existing or current specimens will be centrally performed to uniformly characterise the study population.
 
All successfully screened patients will be randomised in a 2:1 fashion to undergo PRRT with <math>^{177}\text{Lu}</math>-edotreotide or everolimus treatment, respectively, and will be followed-up for outcome for a maximum of 30 months.

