- (AA) (Pre-dose) procedures (e.g. MRT / CT) may be performed within 7 days before visit. Investigations should be performed as close to PRRT as organisationally possible and as clinically appropriate.
- (AAA) Blood-sampling can be performed up to 72 hours prior to the visit according to local practice and as clinically appropriate.
- (B) Bi-weekly controls of haematology for 8 weeks following Lu-Edotreotide administration, to occur in week 2, 4, 6, 8 post dosing (GP acceptable).
- (C) Tumour biomarkers in serum: chromogranin-A (CgA) in all patients; disease-specific hormones, if positive at baseline work-up.
- (D) Pregnancy test for all premenopausal female patients during screening. To be repeated, if dosing starts >14 days after screening. To be repeated monthly until EOS.
- (E) All scheduled evaluations may be performed 72 - 96 h (± 3 h) post infusion.
- (F) Mandatory, unless prior tumour specimen (paraffin block) available. Biopsy sample to be sent to CPL before randomisation.
- (G) Local histopathology report to be sent to the CPL with the biopsy sample.
- (H) Somatostatin agonists (SSA) for symptom control are allowed, if a) not exceeding the licensed posology and b) sufficient wash-out prior to Lu-Edotreotide dosing is observed (24 h for immediate, 28 d for sustained release galenics).
- (I) SRI using PET/CT, SPECT/CT or planar imaging, as locally authorised (by Ga-Edotreotide, Ga-DOTATATE, In-pentetreotide, or 99mTc-octreotide) within 4 months prior to randomisation.
- (K) MRI / CT showing radiological tumour progression based on RECIST 1.1 as evidenced by two scans obtained within a maximum of 36 months prior to randomisation, with at least 90 days interval between them. The most recent scan should not be older than 90 days at randomisation.
- (L) One native liver and contrast-enhanced liver and 3 regional (pelvis, abdomen, thorax) MRI or CT, not older than 28 days at the time of randomisation. Baseline method must be followed throughout the study period.
- (M) 99mTc-MAG-3 renogram to be performed within 28 days prior to randomisation; 7 days prior to administering the cycle D3 (month 6) dose; and if the predicted absorbed kidney dose likely exceeds 23 Gy but not 29 Gy prior to dose D4 (month 9). To be performed within 7 days prior to month 12, 18, and 24 visits.
- (MM) See Sections 5.4.1.2 and 5.4.3 of the protocol for details on dosing after Cycle 1.

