Lu-edotreotide dosimetry will be centrally analysed for the absorbed kidney and target tumour doses in a standardised fashion. Resulting mandatory prescriptions for additional 99mTc-MAG3 renal scintigraphy before continued administration of Lu-edotreotide doses D2 - D4, ensuring a safe kidney dose exposure, will be derived and communicated to the sites by the central lab. Dosimetry will be performed according to the current regulatory standard (conventional planar (2D) dosimetry), and according to the emerging clinical standard (2D/3D hybrid dosimetry) for a more accurate determination of the kidney dose.

Quantitative SPECT reconstruction is a recent option to directly derive quantitative information on Lu activity distribution *in vivo*, allowing to assess absorbed doses to kidneys (safety) and tumour (efficacy) with higher accuracy, compared to planar scintigraphy. In selected study sites, Lu-edotreotide SPECT/CT (3D) will be performed at each time point in addition to planar scintigraphy (2D). Data will be quantitatively reconstructed, and dosimetrically analysed in comparison to planar (2D) and hybrid (2D/3D) dosimetry (Sub-study B).

To assess in-vivo stability of  $^{177}\text{Lu}$ -edotreotide, urine will be collected from all voids beginning immediately post-dose to 1 hour, and in intervals of 1-6, 6-24 and 24-48 hours post-injection in a subgroup of 20 patients at selected sites only. Urine will be analysed using gamma counting and radio-HPLC in order to investigate the radiochemical purity of the eliminated compound, as well as the excretion pattern of  $^{177}\text{Lu}$ -edotreotide (Sub-study C). In addition, bone marrow dosimetry will be assessed in Sub-study C by measuring radioactivity in blood samples at pre-defined intervals from 0 minutes to 7 days post-injection of  $^{177}\text{Lu}$ -edotreotide.

Following administration of each  $^{177}\text{Lu}$ -edotreotide dose (D1 – D4), blood has to be drawn for safety laboratory examinations (haematology) in 2-weekly intervals for 8 weeks. Where these time points will not coincide with formal study visits, blood may be drawn in local medical institutions, if a visit of the study site is not reasonably feasible.

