Everolimus: Patients randomised to everolimus therapy will undergo out-patient visits only. Patients will receive a standard dose of 10 mg daily, which may be reduced, where required for acceptable tolerability, according to manufacturer's product information (see [Appendix 4](#)).

Both study arms: Study visits will be monthly in the first 12 months, thereafter 3-monthly until end of study at month 30 or until progression (whatever occurs first). For symptom control, all patients are allowed to receive somatostatin analogues (SSA), as clinically indicated (best supportive care) in required doses, not to exceed licensed doses. In the  $^{177}\text{Lu}$ -edotreotide arm, clinically established wash-out periods prior to  $^{177}\text{Lu}$ -edotreotide dosing have to be considered (1 day for immediate release, and 28 days for sustained release SSA).

Safety, tolerability and symptom control parameters, as well as tumour markers are captured at regular intervals.

To assess efficacy, serial morphological imaging, comprising native liver and contrast-enhanced liver and 3 regional (pelvis, abdomen, thorax) MRI or CT (see Clinical Imaging Manual for details), is scheduled every three months, consistently using baseline methods. Evaluation of tumour response will be performed by local investigators using RECIST 1.1 criteria.

In case of clinically suspected tumour progression, investigators may schedule appropriate diagnostic imaging at any time.

Image analyses will also be conducted centrally. For establishment of PFS (primary endpoint) blinded reading in duplicate, with adjudication in case of discordance will be used.

Patients who progressed under everolimus may be offered  $^{177}\text{Lu}$ -edotreotide therapy based on the personal judgement of the Investigator, if he/she considers it appropriate and likely to be beneficial for the individual patient (see Section [7.4.2](#)).

To further evaluate tumour response, the tumour marker Chromogranin A (Cg-A) will be determined at baseline, and then monthly until month 12, thereafter in 3-monthly intervals until diagnosis of progression or end of study. Cg-A represents a secretory protein present in dense-core vesicles of neuroendocrine (NE) cells. It is being expressed in most secretory, but also non-functional NET. Cg-A is the best circulating neuroendocrine marker available up to now for the management of differentiated

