### 6.1.3 Scheduled Nephroprotective Amino-Acid Solution for Patient Management

Nephroprotective AAS aims to reduce the risk of acute and chronic radiation nephropathy, by inhibiting undesired renal  $^{177}\text{Lu}$ -edotreotide uptake, thereby allowing administration of higher therapeutic doses to the tumour. Efficient nephroprotection, therefore, does increase the therapeutic index of PRRT. To ensure comparable safety and efficacy of a given therapeutic dose across sites in the present study, a standardised nephroprotection protocol will be used, which is based on the concomitant administration of an amino acid solution (AAS) according to the recommendations of different international Societies of Nuclear Medicine for the management of PRRT in NET (Bodei et al., 2013).

No commercially available amino acid solution, optimised for nephroprotection in PRRT exists. Available products vary considerably in their composition in different countries. For the study, therefore, a standardised amino acid solution optimised for PRRT will be used.

The AAS to be used in this study will contain a mixture of 25 g lysine-HCl and 25 g arginine-HCl diluted in 2000 mL of electrolyte solution, infused over 4 - 6 h, starting 30 – 60 min before PRRT. The AAS should preferably be co-infused with the radiopeptide via a three-way stop cock.

Amino acid infusion causes elevation of serum potassium levels due to induction of a shift of potassium ions from cells to the extracellular department. This shift can lead to significant hyperkalaemia in up to 19% of patients (Giovacchini et al., 2011). In this trial potassium levels are monitored at pre-dose, 4 - 6 h, and 24 h post  $^{177}\text{Lu}$ -edotreotide infusion. If hyperkalaemia  $>6.0$  mmol/l occurs, additional monitoring and/or therapeutic measures should be undertaken. Severe hyperkalaemia can lead to cardiac arrhythmias and subsequently circulatory arrest. Non-specific clinical signs include malaise, palpitations, muscle weakness and mild hyperventilation. Treatment options are e.g. IV calcium, IV loop diuretics (e.g. furosemide), inhaled salbutamol, and oral sodium polystyrene sulfonate/sorbitol.

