### Post-Treatment (only Lu-edotreotide group):

#### Assessments:

- Vital signs immediately after end of infusion and 6 h ± 1 h post start of infusion
- Serum chemistry 5 h ± 1 h post start of infusion
- Concomitant medications and SSA medications continuously
- Adverse events continuously

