#### **7.3.2 Month 1 and Month 2**

The visits have to be performed at day 30 and 60 with  $\pm 7$  days window calculated from day 0.

The following examinations and procedures will be performed in all patients:

- Physical examination
- Vital signs
- Clinical laboratory tests
  - Haematology
  - Serum chemistry and clotting parameters
  - Urinalysis
- Tumour serum biomarker tests
- Pregnancy test
- EORTC QLQ-C30 and GI.NET21
- Concomitant medications and SSA medications continuously
- Adverse events

- Everolimus patients receive their compliance diary

Blood-sampling can be performed up to 72 hours prior to the visit according to local practice and as clinically appropriate.

### 7.3.3 Month 3

It must be noted that if the predicted absorbed dose to the kidneys in patients receiving  $^{177}\text{Lu}$ -edotreotide is likely to exceed 23 Gy upon administration of the next PRRT cycle, dosing can be continued up to a maximum of 29 Gy, provided that a pre-PRRT TER ( $^{99\text{m}}\text{Tc}$ -MAG3 renal scintigraphy) is >50% of the value at baseline (see Sections 3.1, 5.4.1.1, and 5.4.3.2) and the criteria for continued administration of study drug are fulfilled (see Section 5.4.1.2).

#### 7.3.3.1 Day 90

Visit may be performed  $\pm 14$  days calculated from day 0, whereby days 91 and 93 will be calculated from the actual day 90 visit date. Pre-dose procedures may be performed within 7 days before the Day 90 visit for both treatment groups. Investigations should be performed as close to PRRT or dosing as possible and as clinically appropriate.

The following examinations and procedures will be performed:

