8.4 Clinical Laboratory Evaluations

Haematology: haemoglobin, haematocrit, mean corpuscular volume (MCV), mean corpuscular haemoglobin (MCH), white blood cell count (total and differential: leukocytes, neutrophils, eosinophils, basophils, lymphocytes, monocytes), red blood cells, platelets.

Biochemistry: sodium, potassium, chloride, calcium, glucose, creatinine, urea, albumin, total bilirubin, aspartate transaminase (AST), alanine transaminase (ALT), alkaline phosphatase (AP), gamma-glutamyl transferase (GGT), lipase, amylase, total protein,.

Clotting parameters: prothrombin time (quick), reagent-independent prothrombin ratio (international normalised ratio; INR), activated partial thromboplastin time (aPTT).

Urinalysis: specific gravity, pH, protein, glucose, blood, leukocytes, ketones, nitrite, albumin, creatinine; α -1-microglobulin will also be tested in urine but only in centres with adequate technical equipment and an established test method.

Tumour markers: Chromogranin-A, further markers

All lab parameters will be summarised by visit and treatment arms as continuous data (raw and change from baseline) or category data where appropriate (e.g. urine test with category units).

The following parameters will also be presented as boxplot graphs by visit and treatment arm: WBC, RBC, HB, Neutrophils, Lymphocytes, Platelets, alkaline phosphatase, bilirubin, AST, ALT, albumin, potassium, sodium, calcium, and tumour markers.

For the following parameters the percentage of patients experiencing CTCAE toxicity will also be summarised by worst CTCAE grades (all grades pooled and Grades 3 and 4 pooled) and by treatment arm for baseline and post first IMP dosing parts of the study:

ITM-LET-01	Statistical Analysis Plan
------------	---------------------------

Table 6: List of laboratory parameters to be analysed according to CTCAE guidelines

Lab parameter	CTCAE term:
Lymphocytes	Lymphocyte count increased
	Lymphocyte count decreased
Hb	Anaemia
Leukocytes	Leukocytosis
	White blood cell decreased
Platelets	Platelet count decreased
PNN	Neutrophil count decreased
Creatinine	Creatinine increased
Fasting blood glucose	Hypoglycaemia
	Hyperglycaemia
Calcium	Hypocalcaemia
	Hypercalcaemia
Potassium	Hypokalaemia
	Hyperkalaemia
Sodium	Hyponatremia
	Hypernatremia
GGT	GGT increased
Alkaline Phosphatase	Alkaline Phosphatase increased
AST	AST increased
ALT	ALT increased
Total bilirubin	Blood bilirubin increased
Albumin	Hypoalbuminemia

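### SAP 8.4 tabulates worst CTCAE laboratory grade by arm from unequal scheduled sampling (20 versus 12 draws in months 0-11), and no grade table at common visits is planned in the SAP text

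*SAP*

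**What the plan says.** SAP 8.4 (Clinical Laboratory Evaluations) states that for the parameters in SAP Table 6 "the percentage of patients experiencing CTCAE toxicity will also be summarised by worst CTCAE grades (all grades pooled and Grades 3 and 4 pooled"), by treatment arm, separately for baseline and for the time after first dosing. It sets no visit restriction and makes no allowance for the number of samples. The same section plans continuous summaries by visit and arm, and boxplots by visit and arm for the main blood counts, liver tests, electrolytes and tumour markers.

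The sampling schedules differ by arm:

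- **Both arms.** "Study visits will be monthly in the first 12 months, thereafter 3-monthly until end of study at month 30 or until progression" (Protocol 3.1).
- **PRRT only, haematology.** After each dose "blood has to be drawn for safety laboratory examinations (haematology) in 2-weekly intervals for 8 weeks" (Protocol 3.1). Footnote B of Protocol Table 1 fixes these controls "to occur in week 2, 4, 6, 8 post dosing (GP acceptable").
- **PRRT only, chemistry.** "Serum chemistry 5 h ± 1 h post start of infusion" on the dosing day (Protocol 7.3.1.1) and again at about 24 h (7.3.1.2). Both are repeated at later cycles (7.3.3.1, 7.3.3.2, 7.3.5, 7.3.7). Footnote X of Table 1 allows further chemistry if potassium is raised.

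Protocol 6.1.3 says of the potassium effect of the amino-acid infusion: "This shift can lead to significant hyperkalaemia in up to 19% of patients".

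**The concern.** A worst-grade summary is a maximum over a patient's samples. It cannot fall as samples are added, and it usually rises. If one arm is sampled more often, and partly at times when a change is expected, its percentage with any graded value, or with grade 3-4, can be higher even where the underlying risk per sample is the same. A short-lived fall in counts on everolimus may also go unseen between monthly visits.

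At stake is how the laboratory safety tables are read. Protocol 1.3 anticipates better safety and tolerability than everolimus, so readers will set the two columns side by side. Protocol 8.3.2.3 also has clinically relevant laboratory abnormalities recorded as adverse events, so unequal ascertainment can carry into those tables. PFS, ORR and OS are not affected.

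**Working it through.** **Step 1. Reproduce the planned number of draws.** Protocol Table 7 gives, for months 0-11, 20 haematology, 20 biochemistry and 12 clotting samples, not split by arm.

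- Monthly visits, months 0 to 11: 12 samples in either arm.
- PRRT counts: the regimen is described as "consisting of a maximum of four cycles", with controls at weeks 2, 4, 6 and 8, so 4 × 4 = 16 time points. For months 1 and 2, "The visits have to be performed at day 30 and 60 with" a 7-day window (Protocol 7.3.2), and later inter-dose visits have the same window. Weeks 4 and 8 (days 28 and 56) fall inside these windows. Weeks 2 and 6 do not. Over four cycles this leaves separate draws on days 14, 42, 104, 132, 194, 222, 284 and 312, which is 8 extra.
- Haematology: 12 + 8 = 20.
- Chemistry: 12 + 4 × 2 (5 h and 24 h) = 20.
- Clotting has no PRRT-only draws: 12.
- Volume: 3 × 28 + 7.5 × 28 + 3 × 20 + 7.5 × 6 = 399.0 mL, or 406.5 mL with the optional sample.

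All of these match Table 7, so its 20 is the PRRT schedule. The everolimus figure is 12 for each.

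**Step 2. Samples that feed the worst grade.** The day 0 pre-dose sample is baseline (SAP 5.6). Post-baseline draws in months 0-11 are then 19 (PRRT) and 11 (everolimus). Adding the 7 later visits in Table 7 gives 26 and 18 for a patient followed to month 30.

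**Step 3. Effect of sampling alone.** Give both arms the same assumed probability p of a graded value per sample. With k independent samples, P(at least one) = 1 − (1 − p)^k. At p = 1%:

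- everolimus: 1 − 0.99^11 = 10.5%
- PRRT: 1 − 0.99^19 = 17.4%

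With within-patient correlation ρ, a beta-binomial with a = p(1 − ρ)/ρ and b = (1 − p)(1 − ρ)/ρ gives P(at least one) = 1 − B(a, b + k)/B(a, b). Results for months 0-11, everolimus versus PRRT:

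| p per sample | ρ = 0 | ρ = 0.1 | ρ = 0.5 |
|---|---|---|---|
| 0.25% | 2.7% vs 4.6% | 1.9% vs 2.6% | 0.8% vs 0.9% |
| 1% | 10.5% vs 17.4% | 7.2% vs 10.1% | 3.0% vs 3.5% |
| 5% | 43.1% vs 62.3% | 31.6% vs 41.5% | 14.2% vs 16.4% |

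Over p from 0.25% to 5% and ρ from 0 to 0.5, the PRRT:everolimus ratio runs from 1.16 to 1.71 in months 0-11 (gap 0.1 to 19.1 points). To month 30 it runs from 1.09 to 1.43 (gap 0.1 to 13.4 points).

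**Step 4. Common visits.** Restricted to visits scheduled in both arms, each arm has 11 post-baseline samples in months 1-11. The sampling-only difference is then zero for any p when follow-up is equal.

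**The case against.** **Like-for-like views already exist.** SAP 8.4 plans by-visit summaries and boxplots, and the worst-grade table comes in addition to them. That stands. It would be wrong to say that no display uses comparable time points. What is missing is a CTCAE-grade display at such time points. The TFL tracker (SAP 13) is not in the public text and may separate the samples, so the point is limited to what the SAP text says.

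**Much of the excess may be real.** This also stands in part. The amino-acid solution belongs to the PRRT regimen and has no everolimus counterpart, so a peri-infusion potassium rise is an expected effect of that regimen. Week 2 and 6 counts can show true nadirs. A reader might infer that any PRRT excess is produced by sampling alone, but the documents do not support that.

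**Stronger figures are tempting but unsupported.** Compounding 19% over four infusions gives 1 − 0.81^4 = 57%, but the protocol's 19% is of patients and no per-infusion rate is given. A reader might also assume 2-weekly counts throughout, so that a 14-day fall is never missed. The counts stop at week 8 of a cycle of about 90 days. With uniform onset and five draws per cycle (days 14, 28, 42, 56 and 90), a 10-day fall is caught with probability 50/90 = 0.56 and a 14-day fall with 70/90 = 0.78. The durations are themselves assumed.

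**A common-visit table has its own bias.** PRRT is pulsed, and visits at about days 30, 60 and 90 after dosing miss some true nadirs. That stands, and it is why such a table should not replace the all-samples one.

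**The real imbalance may differ from the schedule.** Everolimus interruptions until recovery (Appendix 4) imply repeat counts, and extra visits are allowed at any time (Protocol 8). This is a reason to report the samples actually taken.

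**Conclusion.** The point holds as an improvement to a descriptive table. The scheduled counts are firm for a patient who receives all four cycles on time: 20 versus 12 for both haematology and chemistry in months 0-11. Fewer cycles shrink the gap, and discretionary potassium follow-up widens it for chemistry. The direction of the sampling effect is also firm, since extra samples can raise a worst-grade percentage but cannot lower it.

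The size is not known from the documents. It depends on assumed per-sample risk and within-patient correlation, and is close to nil when abnormalities persist between visits. The independent-samples results are an outer case, since 5 h and 24 h values after the same infusion are unlikely to be independent. SAP 8.4 plans no between-arm test on the worst-grade table, and no confirmatory endpoint is touched.

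**What to change.** In SAP 8.4, keep the all-samples worst-grade table as planned and add:

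1. a worst-grade table by arm restricted to visits scheduled in both arms (monthly in year 1, then 3-monthly, and EOS), using the pre-dose sample on dosing days;
2. a separate PRRT-only display of the inter-visit counts and the 5 h and 24 h chemistry;
3. the number of samples per patient by arm, for haematology and chemistry.

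The cost is SAP wording and one extra table set, with no new data. The common-visit table removes the difference in scheduled sampling frequency but misses some true PRRT nadirs, so a footnote should say that it is to be read beside the all-samples table. It does not correct for unequal follow-up, because visits stop at progression. The per-patient sample counts will make that visible.
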